## **2. Concise summary of project:**

This trial will be a comparative non-blinded randomized controlled trial in obese postpartum women.

Three groups will be compared during the postpartum period:

1. Control Group: Standard of Care

2. Intervention A: Low carbohydrate diet with printed materials and online resources, provided by X-PERT weight loss program.
3. Intervention B: Low carbohydrate diet with a behavioral component consisting of twelve weekly meetings with an X-PERT trained professional supported with printed materials and online resources.

The number of subjects studied will be 321 subjects at UTMB.

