Additionally, subjects enrolled in Intervention B will have 12 weekly group sessions with an X-PERT trained professional. The group sessions will last approximately 1.5 hours and have no more than 20 subjects enrolled in each group. Subjects will be welcome to bring their infant to each group session. A babysitter will not be provided

so the subject will be responsible for taking care of her own infant. Breastfeeding or formula feeding during the group session will be encouraged. The group session is available to research study participants only; besides the infant, no additional family members will be allowed. If enrolled in Intervention B, subjects will have up to 15 in person visits.

Blood and urine samples will be collected at each study visit. The first study visit will occur at 2-3 weeks postpartum. The second study visit will occur at 3 months postpartum (+ 3-week window). The third study visit will occur at 6 months postpartum (+ 3-week window). All samples will be collected while the patient is fasting (not eating for at least 8 hours). A standard 4oz sterile urine collection cup will be provided for each urine sample. Urine will be checked for glucose and ketones by dipstick. Approximately 20mL of blood will be collected with each sample. The blood samples will be used for the following tests:

- Hemoglobin A1c (HgA1c)
- Lipid panel
- Homeostatic Model Assessment (HOMA) test for insulin sensitivity or resistance: we will measure fasting insulin and glucose levels. Fasting will be defined as the last meal more than 8 hours before testing (i.e. overnight fasting). We will be using the following computation to calculate HOMA.

$\text{HOMA-IR} = \frac{\text{Glucose} \times \text{Insulin}}{22.5}$	$\text{HOMA-IR} = \frac{\text{Glucose} \times \text{Insulin}}{405}$
$\text{HOMA-}\beta = \frac{20 \times \text{Insulin}}{\text{Glucose} - 3.5} \%$	$\text{HOMA-}\beta = \frac{360 \times \text{Insulin}}{\text{Glucose} - 63} \%$
Glucose in Molar Units mmol/L	Glucose in mass units mg/dL

Blood and urine samples will be taken to the lab to complete the above-mentioned tests and/or stored at -80°C in our perinatal research department for later processing. The blood and urine will be stored in the perinatal research department with the potential for future metabolic testing that relates to this research study. Only the PI and research staff involved with this study will have access to the stored samples.

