#### **Secondary outcomes:**

- Maternal weight gain: change from baseline body weight at 3 months and at 6 months
- Development of diabetes postpartum (based on a fasting plasma glucose test >99mg/dL or the 75-g, 2-hour OGTT > 199mg/dL)
  - Initiation (if newly diagnosed postpartum) or continuation/restarting (if had gestational diabetes and now diagnosed as diabetes mellitus) of insulin and/or oral medications
- Worsening blood pressure in the postpartum period
  - Blood pressure:  $\geq 140/90$  mm Hg or use of anti-hypertensive medication or increased dose of anti-hypertensive medication
- Other metabolic issues (e.g., thyroid disease, fatty liver disease etc.) discovered through chart review)

The primary outcome (insulin sensitivity/resistance) will be evaluated via the HOMA insulin sensitivity or resistance tests.

Secondary outcomes will be reviewed as follows:

1. Maternal weight gain: Change from baseline body weight at enrollment of study as compared to body weight at 3 month postpartum study visit and 6 month postpartum study visit.
2. Development of diabetes postpartum: As part of routine postpartum care, women at risk for development of diabetes postpartum are evaluated with a fasting plasma glucose test or 2 hour oral glucose tolerance tests. These tests are part of routine clinical care (when indicated) and will be accessed by the research staff through chart review.
3. Worsening blood pressure in the postpartum period: Blood pressure recorded at the time of enrollment to the blood pressure recorded at the 3 month postpartum study visit and 6 month postpartum study visit will be compared. The addition of an anti-hypertensive medication or increased dose of an anti-hypertensive medication will be accessed by the research staff through chart review.
4. Other metabolic issues, such as thyroid disease, fatty liver disease, etc: Additional metabolic issues will be reviewed by the research staff through chart review.

The PI will review and validate the diagnosis for all subjects identified to have the primary outcomes. These reviews will be conducted masked to treatment group. If there is uncertainty, a co-investigator will review the chart and discuss with the co-investigators as needed and make a final determination regarding the outcome.

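### The only masked outcome review is assigned to the primary outcome, a computed HOMA value with no diagnosis to validate, and no masking is stated for the chart-abstracted secondary outcomes

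*Combined protocol and SAP*

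**What the plan says.** Section 2 sets the design: "This trial will be a comparative non-blinded randomized controlled trial in obese postpartum women".

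In Section 3.4, the text under the secondary outcomes first returns to the primary: "The primary outcome (insulin sensitivity/resistance) will be evaluated via the HOMA insulin sensitivity or resistance tests". Section 3 explains how: "we will measure fasting insulin and glucose levels", which then enter the printed HOMA formulas.

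Section 3.4 next takes the four secondary outcomes in turn. On diabetes testing it says: "These tests are part of routine clinical care (when indicated) and will be accessed by the research staff through chart review". Antihypertensive additions and dose increases are also obtained from charts by research staff. On thyroid disease, fatty liver disease and the like it says: "Additional metabolic issues will be reviewed by the research staff through chart review".

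The section closes with the review rule, which opens as follows: "The PI will review and validate the diagnosis for all subjects identified to have the primary outcomes". On whether the reviewers may know the arm, the rule adds: "These reviews will be conducted masked to treatment group". Doubtful cases go to a second reader, who settles them, and here the wording is: "If there is uncertainty, a co-investigator will review the chart and discuss with the co-investigators as needed".

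**The concern.** The review rule is the only statement in the documents that any outcome assessment is masked. It is attached to an outcome that nobody can be identified as having, because HOMA is a number for every woman sampled. The outcomes for which someone reads a chart and decides whether an event counts are not named in the rule.

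In an open-label trial, staff who know the arm may search charts more or less thoroughly, or resolve borderline entries differently, from one arm to another. That could produce or hide a difference between arms in the secondary outcomes. The risk is greatest where the outcome has no written definition.

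**Working it through.** The point is about wording and procedure, so the main check sets the sections side by side.

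**1. Is there a diagnosis in the primary outcome?** Section 3 gives HOMA as arithmetic on two assay results and states no threshold. Section 12 treats HOMA-IR as continuous: it powers an ANOVA on group means of 1.4, 1.05 and 1.05 with within-group variance 0.8. A validated diagnosis, and a chart review to settle uncertainty, have no object here.

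**2. Which outcomes could use a masked chart review?**

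| Secondary outcome | Source | Definition in Section 3.4 | Masking stated |
|---|---|---|---|
| Body weight change | Measured at study visits | Numeric | No |
| Diabetes | Routine-care tests read from charts, done when indicated; start or continuation of treatment | Numeric glucose cut-offs; treatment recorded | No |
| Worsening blood pressure | Study-visit readings; medication changes from charts | Numeric cut-off; medication component | No |
| Other metabolic issues | Charts | Examples only, open-ended | No |

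Room for abstractor judgement is largest in the last row. It is smaller for diabetes and medication changes, and does not arise for weight or blood pressure measured at visits.

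**3. Can the people reading the charts know the arm?** Section 3 has the PI, co-investigator and research coordinators review records for outcomes up to 2 weeks after the final visit. Section 3.1 (Randomization) supplies the allocation scheme to the study coordinator and keeps a log linking group to name and record number. So at least one role that reviews charts also holds the allocation. Section 3 withholds online-application data from researchers at study visits, but that does not hide the arm during abstraction.

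**4. Does the rule reach unrecorded events?** It covers women already identified with an outcome. Even redirected to the chart outcomes, it would test recorded events and not look for events missed in one arm.

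**5. Is the primary analysis affected?** The plan's figure reproduces and does not depend on the review:

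- Grand mean = (1.4 + 1.05 + 1.05)/3 = 1.1667.
- Sum of squared deviations = 0.2333² + 2 × 0.1167² = 0.0817.
- Noncentrality = 96 × 0.0817/0.8 = 9.8, with 2 and 285 degrees of freedom.
- Power at alpha 0.05 = 0.803, and 96 per group is the smallest size reaching 80%.
- Enrolment: 96/0.9 = 106.7, rounded up to 107 per group; 3 × 107 = 321.

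Changing the review rule alters none of these inputs.

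**The case against.** The strongest reply is that this is a slip of wording. The rule directly follows the list of secondary outcomes and speaks of a diagnosis, of outcomes in the plural and of reviewing the chart. All of that fits the clinical outcomes and not HOMA, so masked review of clinical diagnoses was probably intended. This stands as a reading of intent. It does not remove the need for a change, because staff will follow the sentence as written.

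A reader might infer more than the documents support, in four ways.

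- **That chart abstraction is planned as unmasked.** The documents never say so; they are silent. The supportable statement is that masking is not stated.
- **That all the chart outcomes are soft.** Diabetes and blood pressure have numeric cut-offs, and a drug start or dose increase is a recorded fact reflecting the treating clinician's decision. Only other metabolic issues is truly open-ended.
- **That missed events are never checked.** Section 3 has several roles reviewing records for outcomes, and Section 9 has abstraction and data entry monitored, with discrepancies corrected against source documents. These checks are not stated to be masked, but they are not confined to women already identified.
- **That the bias can be sized.** Assuming a different capture rate in each arm gives an apparent risk ratio that merely restates the assumption. The documents give no capture rates and do not fix the direction: Intervention B involves up to 15 in-person visits, and the extra contact could raise detection instead of lowering it.

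Two further points stand. HOMA values still merit some check, since they depend on fasting and on the visit window. And Sections 3 and 9 already store data under an ID code, so masking the laboratory to arm would be a small clarification.

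**Conclusion.** The point holds as a correctable mismatch. The one masked review is assigned to an outcome with no diagnosis to validate, while masking is not stated for the outcomes abstracted from charts in a non-blinded trial. The conclusion rests on reading the rule literally and on the absence of any other masking statement.

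Its reach is limited to the chart-based secondary outcomes, chiefly other metabolic issues, and no numerical size can be given. Masked abstraction would address only the part of the bias that the study team controls. It cannot remove differences arising from unblinded care, such as who is tested when testing is done only if indicated. A reader should not infer that the primary comparison is compromised; its analysis and sample size are untouched. This is a low-priority but worthwhile change.

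**What to change.** In the closing paragraph of Section 3.4:

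1. Replace the reference to primary outcomes with the chart-based secondary outcomes: diabetes tests and treatment, antihypertensive additions or dose increases, and other metabolic issues. Give the last a written definition.
2. Carry out the review on chart extracts with arm and group-session information removed, by investigators or staff already on the study who have no access to the randomization log. If the PI has that access, the review should pass to someone who does not.
3. If feasible, include a sample of women with no recorded event, so that under-recording can be seen as well as over-recording.
4. For HOMA, replace diagnosis validation with data-quality checks on fasting status, visit window and assay values, made without knowledge of arm.

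This mostly redirects a review already planned. The cost is a small amount of time to prepare masked extracts, rising with the number of non-events sampled. The documents give no figure for that time.

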#### **4. Criteria for inclusion of subjects:**

- Maternal age  $\geq 18$  years and  $<50$  years
- Delivery at UTMB
- BMI  $\geq 30$  kilograms/meters at the final prenatal visit prior to delivery
- Singleton gestation
- Accessibility to the internet
- A basic understanding and comprehension of the English language to be assessed by study personnel at the time of recruitment of the study.

As part of the consenting process, an assessment of comprehension and understanding of the English language will be performed. The potential subject will be given a sample of the X-PERT printed document. The potential subject will provide written answers to three questions about the sample material.

Understanding and comprehension of the English language will be assessed by the research staff consenting the patient for the study. The potential subject will be required to answer all three questions correctly in order to be a potential candidate for the study.

#### **5. Criteria for exclusion of subjects:**

- Enrolled in another trial that may affect outcome
- Subject who is unlikely to be followed-up after delivery

- Diabetes mellitus on medication; gestational diabetes requiring medication at the recruitment visit
- Other serious medical condition at the discretion of the PI (e.g., heart failure, kidney failure, severe asthma)
- Planned pregnancy during study period

## **6. Sources of research material**

Electronic medical chart/records, blood samples, questionnaires.

## **7. Recruitment Methods and Consenting Process:**

Please refer to section 3.1 above.

## **8. Potential risks:**

### **8.1. Randomization Risk**

Since the diet regimen will be randomized, it is possible that one or more of the other treatment groups will have more benefit than the group to which subject is assigned.

### **8.2. Loss of Confidentiality**

Any time information is collected, there is a potential risk for loss of confidentiality. Every effort will be made to keep the subject's information confidential; however, this cannot be guaranteed.

### **8.3 Blood Draw Risk**

Each subject will have three blood draws collected throughout their participation in the study. Risks of taking a blood draw include pain, a bruise at the point where the blood is taken, redness and swelling of the vein, and infection. There is a rare risk of fainting.

### **8.4 Side effects of low carbohydrate diets (Intervention)**

Subjects may experience minor side effects like headache, food cravings at the initiation of a new diet.

## **9. Subject Safety and Data Monitoring:**

The collaborators and research coordinator will be responsible for monitoring the safety of this study. The report will include participant demographics, expected versus actual recruitment rates, summary of any quality assurance or regulatory issues, summary of adverse events (AEs) or serious adverse events (SAEs) which may have occurred, and any changes in the protocol as a result of these issues. The collaborators and research coordinator will monitor for adherence to consent procedures, inclusion and exclusion criteria, valid abstraction, correct entry, timeliness and responsiveness to data queries. Data collection will be identified with a participant ID number. Data will be collected and stored with the participant ID code only. The master enrollment log linking subject identifiers with study ID numbers will be kept in a password-protected database. Several data collection forms will be used. Data on these forms devoid of personal identifiers will be securely stored at our perinatal research division. The

research coordinator and PIs will be available to monitor the data and correct any discrepancies based on source documents if needed.

**10. Procedures to Maintain Confidentiality:**

Each subject will be assigned a study number with personally identifiable information deleted or removed. If needed, charts will be reviewed in the medical records area. Subjects' information will be de-identified and tagged with a number. Data will be collected and stored on a UTMB password-protected computer in a locked room.

**11. Potential benefits:**

Obesity is an evolving epidemic and there is a strong association with consumption of an unhealthy diet. This study may show that the X-PERT program may lead to better maternal outcomes.

**12. Statistical approach:**

Analysis will be performed by intent to treat. Univariable and multivariable analysis will be used to describe the population in the study and to identify potential confounding variable. Standard normality analysis will be used. Demographics and descriptive statistics such as t test, Pearson's chi square, and Mann-Whitney tests will be used as indicated. Data will be either shown as median +/- IQR or mean +/- SDEV as appropriate.

Statistical analyses of primary and secondary outcomes between three groups will be performed by ANOVA or non-parametric equivalent. The statistical method used for power calculation is ANOVA. The sample size was calculated using a superiority trial design using HOMA IR as the primary outcome to measure the overall effect size across the three groups. Based on prior data published (18), we assume effect size of our intervention to be 25% in estimating the group mean of 1.4, 1.05, and 1.05. Assuming within group variance of 0.8, our proposed sample size of 96 per group (total sample size of 288) will reach a power of 80% at alpha of 0.05. Above power calculation was performed by STATA 15.0.

Assuming ~10% loss to follow, this study proposes a total of 321 subjects will be needed to complete the study. This trial will be registered with Clinicaltrials.gov before recruitment is initiated and after IRB approval.

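### Section 12 plans a search for confounders but gives what it finds no role, so the primary model can still be chosen after the data are seen

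*Combined protocol and SAP*

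**What the plan says.** All the relevant statistical text is in section 12 of the combined protocol and SAP (Statistical approach).

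- On covariates: "Univariable and multivariable analysis will be used to describe the population in the study and to identify potential confounding variable". No candidate list, selection rule or timing follows, and nothing is said about what is done with a variable once it has been identified.
- On description: "Demographics and descriptive statistics such as t test, Pearson's chi square, and Mann-Whitney tests will be used as indicated".
- On outcomes: "Statistical analyses of primary and secondary outcomes between three groups will be performed by ANOVA or non-parametric equivalent". No covariate appears here, and the power calculation rests on the same ANOVA.

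Elsewhere, section 3.1 (Randomization) specifies simple randomisation with no stratification, and section 2 says the trial is not blinded.

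**The concern.** Under simple randomisation, baseline differences between the arms as randomised arise by chance. Looking through trial data for confounders is therefore a step borrowed from observational work. It does no harm if it only describes the women. It matters if its product enters the outcome analysis, and section 12 neither says that it does nor rules it out.

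Three things are at stake:

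- **Error rate.** With no stated primary model beyond the ANOVA and no stated role for an adjusted one, an adjusted result could be preferred after both are known. Nothing in the plan masks that choice.
- **Estimand.** The search is not limited to baseline. Section 3.1 records weight, waist and blood pressure at every visit. Section 3 says that data entered in the online application, which only the two diet arms use, will be used in the analysis. Adjusting HOMA-IR for weight or waist measured after the diet began would remove part of the effect under test.
- **Precision.** Measures known before randomisation are available but have no planned use in the outcome model.

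**Working it through.** **1. Reproduce the plan's figure.** Inputs, all from section 12: HOMA-IR means of 1.4 in the control arm and 1.05 in each diet arm, a common variance of 0.8, 96 women in each arm (288 in all), and the target that this design "will reach a power of 80% at alpha of 0.05".

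- Grand mean = (1.4 + 1.05 + 1.05)/3 = 1.1667.
- Sum of squared deviations = 0.2333² + 2 × 0.1167² = 0.08167.
- Noncentrality λ = n × 0.08167 / variance = 96 × 0.08167 / 0.8 = 9.80.
- Noncentral F with 2 and 3 × (96 − 1) = 285 degrees of freedom gives power **80.3%**. With 95 per group it is 79.8%, so 96 is the smallest size that reaches 80%.
- Reading 0.8 as a standard deviation would give 88.6%, so variance is what was used.
- Dropout: 288/0.9 = 320, or 321 when made divisible by three, as stated.

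**2. Error and power under different uses of covariates.** Simulated trials: 96 per arm, planned variance, 8 candidate baseline covariates, 10,000 null and 4,000 alternative runs per scenario. The number of candidates and their correlations with the outcome are assumptions. Scenario A has one covariate with correlation 0.5; B has 0.5, 0.2 and 0.2; C has 0.2 and 0.2. The remaining candidates are unrelated to the outcome.

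| Rule for the reported test | Type I error, A / B / C (%) | Power, A / B / C (%) |
|---|---|---|
| Unadjusted ANOVA | 5.2 / 5.0 / 5.1 | 81.6 / 80.7 / 81.1 |
| Prespecified prognostic covariates | 4.9 / 5.3 / 5.2 | 91.6 / 93.3 / 84.1 |
| Selected by baseline imbalance, p<0.05 | 4.5 / 4.2 / 4.9 | 82.1 / 81.2 / 80.9 |
| Selected by association with outcome, p<0.05 | 4.9 / 5.3 / 5.1 | 91.5 / 93.1 / 83.7 |
| Selected by >10% change in estimate | 5.0 / 5.0 / 5.2 | 90.8 / 91.8 / 83.2 |
| Smaller p of unadjusted and outcome-selected | 7.5 / 8.2 / 6.5 | not comparable |
| Smallest p over all models tried | 9.0 / 10.9 / 8.1 | not comparable |

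Monte Carlo standard error is about 0.2 points for error (√(0.05 × 0.95/10,000)) and at most 0.6 points for power (√(0.8 × 0.2/4,000)). Inflation appears only in the last two rows, where the model is picked by its p-value.

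**3. Precision gain from fixed covariates.** If they explain a share R² of within-group variance, λ = 9.80/(1 − R²). The loss of a few degrees of freedom from 285 is negligible.

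| Assumed R² | λ | Power at 96 per group |
|---|---|---|
| 0 | 9.80 | 80.3% |
| 0.02 | 10.00 | 81.1% |
| 0.08 | 10.65 | 83.6% |
| 0.21 | 12.41 | 89.1% |
| 0.25 (correlation 0.5) | 13.07 | 90.6% |

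The documents give no R² for any covariate.

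**The case against.** The strongest reply is that the plan names one outcome analysis, and it is unadjusted. The sentence on confounders sits with the descriptive statistics and normality checks, and describing the population is the first purpose it gives. A reader might infer that data-selected covariates will enter the primary test; no section says so. **This stands**: the ANOVA as written has correct error and the stated power.

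A reader might also infer that the test must either lose power or exceed 5%. The table refutes that. Mechanical selection stayed at or slightly below 5% within simulation error, and no rule fell below the planned 80% power. Power is lost only relative to a prespecified adjusted model that the sponsor did not plan, and the plan does not propose picking a model by its p-value.

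Three further points deserve weight:

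- Chance is the only source of imbalance among women as randomised, but not necessarily among those analysed. Section 3.3 ends follow-up at withdrawal and replaces women who withdraw before the primary outcome, and section 12 expects about 10% loss. That is a reason to plan for missing data; an undefined confounder search does not deal with it.
- No section proposes adjusting for follow-up weight, waist or medication. The concern is that nothing excludes it.
- The descriptive tests are not said to compare arms, and dropping baseline p-values would change no trial result, so that is not pressed here.

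**Conclusion.** The point holds as a gap in specification that can be closed by wording, not as an error in the planned test. Section 12 sets up a data-driven search and leaves its role undefined, so the primary model is open to later choice. If that choice were made by p-value, type I error would be about 6.5–11% under the assumed covariate structures; under a fixed rule it stays near 5%. That covariates would be chosen after results are known is a possibility left by the silence on timing, not something the plan states.

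The forgone precision is real but of unknown size. Power of about 90% should not be expected from demographic and obstetric covariates: it needs roughly a fifth to a quarter of the variance explained. At an assumed 2–8%, power is 81–84%. The title of reference 18 links ethnicity and gestational diabetes to insulin secretory capacity in pregnancy, which does not establish that they predict postpartum HOMA-IR. Section 5 also excludes gestational diabetes requiring medication at recruitment, which narrows that contrast.

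**What to change.** In section 12:

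1. Remove the confounder search as a basis for adjustment; keep the description of the population.
2. State one primary model for HOMA-IR: a comparison of the three arms adjusted for a few prognostic covariates that are fixed before any outcome is seen and known before randomisation. Candidates are final prenatal BMI (an entry criterion in section 4), gestational diabetes in the index pregnancy, and race/ethnicity (obstetrical history and demographics are collected under section 3). The sponsor may have better ones.
3. Use visit-1 HOMA-IR as a covariate only if it is sampled before the diet starts. Section 3 places that visit at 2–3 weeks postpartum, while section 3.1 (Group assignment/Intervention) implements the intervention once the woman is randomised. The sponsor needs to reconcile the two.
4. State that no post-randomisation variable enters the primary model.
5. Label the unadjusted ANOVA and any other adjusted model as sensitivity analyses.

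The cost is SAP wording, a few degrees of freedom out of 285, and giving up ad hoc adjustment for an unexpected imbalance in the primary analysis; such an adjustment can still be shown as a sensitivity analysis. The sample size need not change.
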